**Description of Non-Health Information That Will Be Viewed or Recorded**

1. Patient and LAR address, telephone number, email address
2. Caregiver address, telephone number, email address

**HIV / AIDS Related Information Will Yes  
Be Viewed or Recorded**

**Informed Consent Will Be Obtained Yes  
to Access Identifiable HIV / AIDS  
Information**

**Data That Will Be Viewed, Yes  
Recorded, or Generated Contains  
ANY of the Following Directly  
Identifiable Information**

**Will Be Viewed** Name, Medical Record Number, Address by street location, Telephone number, Health Plan Beneficiary Number, Account Number, Geographical Subdivisions Smaller Than a State, All Elements of Dates for Dates Directly Related to an Individual (i.e., Birth Date, Admission Date, Discharge Date), Email Address

**Will Be Recorded** Name, Medical Record Number, Address by street location, Telephone number, Health Plan Beneficiary Number, Account Number, Geographical Subdivisions Smaller Than a State, All Elements of Dates for Dates Directly Related to an Individual (i.e., Birth Date, Admission Date, Discharge Date), Email Address

**Data Collection Sheet**

Datasheet for data warehouse and screening.xlsx

***A Data Collection Sheet is required if you are either performing a retrospective review, or your study meets the category of exempt 4 research, or your study meets the category of expedited 5 research. Please upload it here.***

**Data Collection Source(s)**

Participant, Medical Chart (Paper or Electronic), Data Warehouse

**21. Data - HIPAA****Obtaining HIPAA Authorization** Yes**How PHI Will Be Protected from Improper Use or Disclosure**

All data will be recorded stored in a restricted folder on Mount Sinai's secure server. Each person who will work with the data has a unique username and password to log onto the server, and then only these individuals will have access to a folder on the server for the Department of Geriatrics and Palliative Medicine. No data will be stored on local hard drives or movable media (i.e. no data will be stored on flash drives, etc). Any printouts that have PHI (which will be extremely rare) will be stored in locked cabinets in locked offices. All printouts will be destroyed/shredded as soon as they are no longer needed.

**PHI Will Be Destroyed at the Earliest Opportunity Consistent with the Research** Yes**When and How PHI Will Be Destroyed**

We will remove all PHI at the earliest time possible by deleting these variables from the dataset. Any PHI that is printed will be shredded as soon as possible.

**PHI Will Be Shared** No***PI must attest to the following.***

***\* I assure that the protected health information (PHI) will not be disclosed to any other person or entity not listed on this form except where required by law or for the authorized oversight of this research project. If at any time I want to reuse this PHI for other purposes or disclose it to other individuals or entities I will seek approval from the IRB.***

## **23. Data - Storage**

### **Location Where Data Will Be Stored**

Data, obtained from the subject interviews and the clinical record, will be stored in on Sinai's secure server in a restricted-access folder. Access to the database will be restricted to the Principal Investigator, Co-Investigators, study coordinator and data analysts. The database will be maintained on the Mount Sinai Medical School's server which is firewall protected. We are not proposing to analyze the content of the video visits, and thus the video consults will not be recorded, saved, or stored.

All aspects of the intervention will be in the treating record as the intervention is provision of clinical care to patients and their caregivers and it is important that the information is documented within the electronic medical record as it would be for any clinical care. The results of the interviews with patients at baseline will be shared with patients' providers through the EMR.

**How will the data be stored?** Other

### **Specify How Data Will Be Stored**

Data on patients, caregivers, and legally authorized representatives will be stored with identifiers intact. It is necessary to keep these identifiers intact as the data may be subdivided into separate databases for portions of the analyses and these identifiers will be needed to link it back with other portions of the data. All data will be stored on Sinai's secure server that is accessible only through password protected individual logins. Once all of the data analyses are done, the identifiers will be removed from the dataset such that at some point in the research it will become an anonymous dataset stripped of identifiers.

**Research Personnel Responsible for:** [name]

**Accessing Data** Yes

**Receipt or Transmission of Data** Yes

**Duration Data Will Be Stored**

We will maintain our records for three years after closing out the Human Research

**Steps That Will Be Taken to Secure the Data During Storage, Use, and Transmission**

All data will be recorded and stored on Sinai's secure servers in a restricted access folder. Interview data will be recorded using a REDCaP platform on the secure server. All users will have a unique user ID and password to log onto the Sinai server and then only the individuals on this trial will have access to the folder which contains the data files and

PHI associated with them. As soon as possible, all identifiable information is removed from the databases and related files so that PHI is removed from the dataset as soon as possible. No data will be stored on local drives or removable media of any type.

**Power Analysis/Data Analysis Plan (Including Any Statistical Procedures)**

Please see the data analysis plan in the accompanying proposal.

## **24. Data - Safety Monitoring**

**More Than the Minimum Data Safety Monitoring Will Be Done** Yes

**Principal Monitor**

**Additional Monitors**

### **Specific Items That Will Be Monitored for Safety**

All SAEs, regardless of treatment group or relationship to research, will be reported to the IRB within 24 hours in a full written report. Note that these patients have advanced illness and are receiving palliative care. As such deaths will be recorded and regularly reported to the IRB but deaths are not in and of themselves considered SAEs due to the nature of the patient population. We will review each death and evaluate the relationship of that death to any medications prescribed or recommended by the study team. If the team believes there is a causal relationship between the prescription of the medication and the subject's death, this will be reported to the IRB as a serious adverse event.

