### **Safeguards to protect Subjects rights and welfare**

We have undertaken numerous steps to protect patients' rights and safeguard their welfare, in light of their likely impaired capacity.

1. The patient's healthcare provider will introduce the study and determine interest before we approach the patient and caregiver.
2. We will ask the patient's healthcare provider to complete a capacity assessment. Where the patient lacks capacity to consent to study involvement (which we anticipate in most cases) we will follow standard protocol for consent in patients lacking capacity (i.e., their LAR will provide authorization)
3. We will clearly state the dyad's right to refuse participation and to withdraw at any time during the study period without affecting their routine clinical care.
4. The intervention will be provided by a team of highly trained professionals, who have extensive experience in caring for patients with moderate-severe dementia and their caregivers.
5. The procedures undertaken in the patient's home (which may include: clinical examination, recording of vital observations, blood draws, X rays, ultrasound) will be dictated only by the clinical needs identified using standardized assessments. The clinical team will record all encounters with the patient or caregiver in the secure

electronic medical record. Note - as of 3/19/2020 we will no longer be doing home visits as part of the intervention due to the risk of transmission of COVID-19 to a high risk population, with the exception of clinical emergencies that cannot be managed using telemedicine as previously documented.

6. Medications will be prescribed and de-prescribed according to need to treat clinical problems on the basis of clinicians' experience and in accordance with relevant guidelines. In all cases, medications will be prescribed by licensed providers, either the palliative care MD or the palliative care advanced practice nurse. Risks and benefits will be discussed in all cases of prescribing or de-prescribing a medication with the patient where they have capacity, or with their LAR when the patient lacks capacity. Additionally, the provider will communicate all medication changes to the patient's nominated physician.

7. All appropriate measures will be taken to ensure the secure transmission, storage and use of protected health information.

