#### **2. Control subjects**

While control subjects will not receive clinical care, research coordinators will undertake interviews with patients (or proxies) and caregivers at baseline. The results of these interviews will be relayed to the patient's nominated physician. These will serve to highlight previously unrecognized problems. Additionally, caregivers in the control arm will be offered coaching from a health coach on health improvement (e.g., dietary education, smoking cessation). The health coach will be certified in providing health education.

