Frequency of contacts with the team will be individualized according to the dyad's needs. Some assessments will include multiple team members simultaneously while others will be done individually. Intervention dyads receive access to 24-hour telemedicine support, using the pre-existing infrastructure within our Department. We will also use Mount Sinai's 24/7 community paramedic program whereby physicians can dispatch Mount Sinai paramedics to provide in-home treatments without automatic transport to the emergency department. Community paramedicine are operating under guidelines to reduce the risk of COVID-19 transmission.

At the end of their time on the program, the dyad continues care with their usual providers, or is referred onward to other services as appropriate (e.g., Mount Sinai Visiting Doctors, hospice).

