### **Frequency of Data Review**

All adverse events that are both serious and unexpected will be reported to the IRB, NIA PO, and the independent study monitor within 48 hours of the study's knowledge of the SAE. All adverse events will be reported as per the IRB's policies.

The PI and program manager will also report data on enrollment, data collection, adverse events, serious adverse events and unanticipated problems every quarter to the independent safety monitor.

The PI will report all adverse events and serious adverse events every 6 months to the program officer at the NIA. The PI and program manager will meet every week for the duration of the study.

Note that in the first month of the study, [name] and the project manager will review all adverse events/ serious adverse events with the independent safety monitor to ensure they agree with the determinations as to which ones are study related.

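### Adverse events are reported for both arms without a common way of finding them, so counts of events outside deaths, hospitalizations and ED visits are open to detection bias, probably towards the intervention arm

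*Protocol*

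**What the plan says.** **Reporting covers both arms.** Under Specific Items That Will Be Monitored for Safety (protocol section 24), "All SAEs, regardless of treatment group or relationship to research, will be reported to the IRB". Frequency of Data Review adds that "All adverse events will be reported as per the IRB's policies" and that "The PI and program manager will also report data on enrollment, data collection, adverse events, serious adverse events and unanticipated problems every quarter"; the recipient of that quarterly report is the independent safety monitor.

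**Study clinical contact is in one arm.** In section 12, "Intervention dyads receive access to 24-hour telemedicine support", and "Frequency of contacts with the team will be individualized according to the dyad's needs". Community paramedics can also be sent to the home. Under the safeguards in section 8, "The clinical team will record all encounters with the patient or caregiver in the secure" electronic record, and section 23 repeats that "All aspects of the intervention will be in the treating record". For the other arm, section 10 begins "While control subjects will not receive clinical care". Control caregivers see a health coach monthly about a physical health goal of their own.

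**Some sources are shared.** Both arms have interviews at baseline, 3 and 6 months, with a blinded assessor at follow-up. The record is abstracted at those times and after each hospitalization, and data warehouse and claims data are obtained.

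**What counts as an SAE is narrowed.** Section 10, on medication risks, treats hospitalization, death, worsening delirium or function and other serious events as expected in this population and not as SAEs. Section 24 makes a death an SAE only if the team judges it causally related to medication that the study team prescribed or recommended.

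**The concern.** The documents state who is told about adverse events and how quickly, but not how the study learns of them. Where no one asks a standard question, an event becomes known mainly because a clinician was in contact and wrote it down. That contact differs between the arms by design.

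The patient risk that the protocol names first is medication prescribed by the study team, including opioids and antipsychotics. Some plausible harms, such as a fall or sedation at home, may never produce a hospital record. If the monitor or a final report shows more of them in the intervention arm, the excess could be harm or could be observation. The ambiguity runs both ways: surveillance could look like harm, and real harm could be dismissed as surveillance.

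**Working it through.** There is no planned figure to reproduce: the documents give no adverse-event rate, no detection rate and no between-arm safety analysis. The check sets the routes to detection side by side and then sizes the effect under stated assumptions.

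**Step 1. Is there a common question?** The standardized instruments (section 14) cover symptoms, quality of life, burden, depression, satisfaction, resource use, function, comorbidity, agitation, self-efficacy and neuropsychiatric symptoms. The team-made instruments cover demographics, care preferences and financial burden. Follow-up chart review (section 20) covers medications, hospital and ED use, advance care planning and selected treatments. None is listed as an adverse-event item.

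**Step 2. Routes by which an event can become known.**

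| Route | Intervention | Control |
|---|---|---|
| Usual physician's notes | yes | yes |
| 3- and 6-month interview | yes | yes |
| Chart abstraction, warehouse, claims | yes | yes |
| Study nurse, social worker and CHW contacts | yes | no |
| 24-hour telemedicine, paramedics | yes | no |
| Study-team notes in the abstracted record | yes | no |
| Monthly coach | no | yes, on the caregiver's own health |

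Shared chart abstraction does not level this, because the intervention patient's record contains an additional author.

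**Step 3. Which events are affected?** Deaths, admissions and ED visits are found through shared routes. Events managed at home rely more on the unshared ones. Because section 10 takes hospitalization and death out of the SAEs, the evenly captured events leave that count. The one route by which a death returns, study-team prescribing or recommendation, exists in practice only in the intervention arm.

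**Step 4. Size, under assumptions.** With the same true rate in both arms,

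apparent rate ratio = detection probability in intervention ÷ detection probability in control.

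Assume detection of 80–90% in intervention and 40–70% in control:

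- smallest: 0.80/0.70 = 1.14
- between: 0.90/0.70 = 1.29; 0.80/0.60 = 1.33; 0.90/0.50 = 1.80
- largest: 0.90/0.40 = 2.25

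**Step 5. How visible would this be?** The 125 patients randomized 1:1 give about 62 per arm. As an illustration, assume 40% of patients in each arm truly have such an event. The expected number observed is 62 × 0.40 × detection. The chance of a nominally significant two-sided 5% difference is Φ[(p₁ − p₂ − 1.96·SE₀)/SE₁], where p is the observed proportion, SE₀ is the pooled and SE₁ the unpooled standard error.

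| Detection | Expected patients with an event | Chance of a false difference |
|---|---|---|
| 80% v 70% | 19.8 v 17.4 | 7% |
| 90% v 70% | 22.3 v 17.4 | 16% |
| 90% v 50% | 22.3 v 12.4 | 51% |
| 90% v 40% | 22.3 v 9.9 | 72% |

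At a true rate of 20% the chances for 90% v 70% and 90% v 50% are 9% and 25%; at 60% they are 27% and 78%. No such test is planned. The table only shows how easily the counts could look like a signal.

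**The case against.** **The relevant documents were not available.** A trial-specific data and safety monitoring plan dated March 2020 is attached to the protocol and may say how events are elicited. The instruments file is also an attachment, and the protocol gives names and topics, not questions. This stands. What can be said is that the protocol and SAP describe no common method, not that none exists.

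**No comparison is planned.** The SAP has no adverse-event analysis, there are no interim analyses, and deaths are reviewed case by case for a causal link to medication. Nothing says that the quarterly report is split by arm. This also stands: the weakness lies in how the counts could be interpreted, not in a stated test. It does not remove the point, because events are collected from both arms and a final safety table by arm would be a natural use of them.

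**A reader might infer that the arms cannot be compared on safety at all, or that only intervention patients have notes in the record.** The documents do not support either. Every patient must have a physician at a Mount Sinai site, the control baseline assessment is placed in the record, deaths are recorded whatever their SAE status, and hospital and ED use come from shared sources. Only study-team notes are one-sided.

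**A reader might also infer that an intervention-arm excess is certain.** It is a likely direction. Detection rates are not documented, and fewer true events in the intervention arm could offset the bias.

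**Conclusion.** The point holds for events other than deaths, hospitalizations and ED visits. As the protocol is written, their counts depend on a level of clinical contact that differs by arm, and they should not be read as a between-arm comparison. The narrowing of the SAE definition makes this worse for SAE counts.

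The apparent rate ratio of about 1.14 to 2.25 rests entirely on assumed detection probabilities and equal true rates; the documents neither confirm nor contradict those values. The conclusion is also conditional on the unseen monitoring plan not already setting a common method. Nothing here touches the co-primary analyses of SM-EOLD and QOL-AD. The change is worth making because it is inexpensive and bears on the main risk that the protocol names for patients.

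**What to change.** 1. Add a short fixed adverse-event checklist, covering the time since the last interview, to the existing 3- and 6-month interviews. The blinded assessor asks it identically in both arms, **after** SM-EOLD and QOL-AD are complete, so that an answer revealing allocation cannot affect them.
2. Add the same items to the existing record abstraction in both arms, excluding study-team notes and covering the time up to withdrawal or death. Interviews alone would not be enough: patients who die, enter long-term care or stay in hospital beyond 30 days are withdrawn and could miss the next interview.
3. State in the SAP that any between-arm safety summary uses these common-source events. Show events known only through intervention-team or coach contact in a separate column. Expedited reporting stays unchanged.
4. If the data and safety monitoring plan already specifies common elicitation, carry that text into the protocol instead.

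The cost is a few minutes on two existing interviews, one REDCap form and some additional abstraction items, with no new visits. The checklist relies on caregiver recall over 3 months and on caregivers who know their allocation, so reporting bias is reduced but not removed. A small risk of unblinding the assessor remains, including at 3 months for the 6-month interview if the same person conducts both.

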#### **1. Medications (patient subjects only)**

There are risks to patients related to the prescription of medications, particularly those that may be prescribed for pain (including opioids) and behavioral and psychiatric symptoms (antipsychotics). These medications will only be prescribed in accordance with clinical guidance, after careful consideration of the risks and benefits of their use. In particular, we will only use antipsychotics for the management of behavioral symptoms where reversible causes have been considered and treated as appropriate, and the patient is at extreme risk or in severe distress. In all cases where a new medication is commenced we will inform the patient's treating physician and counsel the caregiver about the medication.

Please note that we are enrolling patients with advanced dementia who are by definition at high risk of both worsening delirium and function, hospitalization, death and other serious events. As such these outcomes are expected and will not be considered SAEs.

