### **Description of Procedures Taken to Lessen the Probability or Magnitude of Risks**

Patients in the intervention arm will be cared for by a highly trained team of providers, with experience in caring for patients with dementia and their caregivers. Our intention is to have written communication with the PCP at the time the patient comes on to the program to establish roles within this co-management model of care. As part of this communication, we would include the statement: "Where there is a need to prescribe medications, we will seek your agreement prior to prescribing. However, if we do not receive a response within 48 hours, or the clinical situation demands a more urgent response, we will not await your agreement before prescribing medications. In all cases, we will inform you of our action." This written statement is also included in the Attachments tab.

The research team are highly experienced and all research coordinators will be trained on sensitive interviewing and research protocols.

Any expression of significant mental health issues exposed in a survey response will be discussed with the PI or study manager. We will set thresholds for escalation to the PI based on scores on Zarit Burden Inventory and PHQ-9, any expressions of distress, and any concerns by the study team. The PI or study manager would then contact the caregiver to encourage them to seek additional support from their primary physician and/or the intervention team as appropriate.

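### The death review in Section 24 covers only drugs the study team prescribed or recommended, so a death attributed to a drug the team stopped has no written route to SAE status

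*Protocol*

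**What the plan says.** Protocol Section 8, *Safeguards to protect Subjects rights and welfare*, item 6, describes what the study clinicians do with drugs: "Medications will be prescribed and de-prescribed according to need to treat clinical problems". The same item treats stopping as an act that carries risk: "Risks and benefits will be discussed in all cases of prescribing or de-prescribing a medication". It also has the provider tell the patient's nominated physician about every medication change.

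Protocol Section 24, *Specific Items That Will Be Monitored for Safety*, requires a full written report of every SAE to the IRB within 24 hours. It says that a death is not an SAE merely because it is a death, then sets the review: "We will review each death and evaluate the relationship of that death to any medications prescribed or recommended by the study team". A death is reported as an SAE if the team believes there is "a causal relationship between the prescription of the medication and the subject's death".

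Protocol Section 10, *Medications (patient subjects only)*, lists death among the expected outcomes that will not count as SAEs. It states no exception.

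Protocol Section 24, *Frequency of Data Review*, sends events that are both serious and unexpected to the IRB, the NIA program officer and the independent monitor within 48 hours. All adverse events follow IRB policy. Adverse events, SAEs and unanticipated problems go to the independent monitor each quarter.

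**The concern.** Where deaths are not SAEs by default, the exception decides which deaths are recorded as possible harm from the programme. Here the exception is narrower than the intervention. Item 6 gives the team two kinds of medication action and attaches risk to both, but the death review is written around one of them. The intervention also has non-drug components, such as telemedicine support and physician-dispatched paramedics, and the review names none of these.

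What is at stake is classification and speed of reporting. A death classed as an SAE triggers the 24-hour full report and enters the SAE counts sent quarterly to the monitor and every six months to the NIA. A death outside the exception is recorded and reported to the IRB in the regular way. If the team stops a drug and believes this contributed to a death, the written rule does not move that death from the second group to the first. Anyone who later read the SAE record for intervention-related deaths would be relying on a test that did not ask about one of the recognised exposures.

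**Working it through.** The plan states no figure on this point and no arithmetic applies. The check is to list what the study team can do, then ask of each action whether the text gives a resulting death a route to SAE status.

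**Routes in the text**

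1. *Default.* Section 10 calls death expected and not an SAE. Section 24 says that death alone is not an SAE. Neither provides a route.
2. *Death review and trigger (Section 24).* The review covers drugs prescribed or recommended. The trigger is "causal relationship between the prescription of the medication and the subject's death, this will be reported to the IRB as a serious adverse event". This is the one explicit route.
3. *Serious and unexpected events (Section 24).* This needs an unexpected event. Section 10 has already labelled death expected, so on the protocol's own terms the condition is not met.
4. *Adverse events per IRB policy (Section 24).* This is a general duty to report. It does not classify a death as an SAE.

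**Actions set against those routes**

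| Study-team action | Within the death review? | Within the SAE trigger? |
|---|---|---|
| Drug prescribed by the team | Yes | Yes |
| Drug recommended but not prescribed by the team | Yes | Unclear: the trigger speaks of prescription only |
| Drug continued at a changed dose on the team's prescription | Yes, on a natural reading | Yes, on a natural reading |
| Drug stopped altogether | Not named | Not named |
| Non-drug component of the intervention | Not named | Not named |

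The fourth row is the clear gap, because Section 8 item 6 explicitly makes stopping a team action. The second row shows that the trigger is narrower than the review that feeds it. The fifth row follows from the review being confined to medications. Section 12, *Intervention dyads*, gives an example of a non-drug component: physicians may send paramedics to "provide in-home treatments without automatic transport to the emergency department".

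**Where the stops would be found.** Section 20 lists drug name and dose among the chart-review items, and Section 12 schedules abstraction at baseline, 3 months, 6 months and after each hospitalization. Those lists do not record who stopped a drug. A patient who died at home in month 2 without a hospital stay might have only the baseline list. Sections 8 and 23 place the clinical team's encounters and all aspects of the intervention in the electronic medical record, so that is where a stop and its author would appear.

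**The case against.** The strongest answer is that the rule is permissive and that nothing is hidden. The trigger says what happens if the team finds a causal link; it does not say that no other death may be an SAE. Every death is recorded, reviewed and regularly reported to the IRB. Unanticipated problems reach the independent monitor each quarter. In the first month the study team and the monitor go through all adverse events together to agree which are study related, with no limit to prescriptions. Section 24 and Section 26 also list a data safety monitoring plan, which is not in the file and may define relatedness more broadly.

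Much of this stands, and it rules out several stronger readings:

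- A reader might infer that such a death can never be an SAE. The text supports only that no route is written, because the condition is stated as sufficient and not as exclusive.
- A reader might infer that the study team decides against hospital transport. Section 12 says only that transport is not automatic. It does not say that the team orders non-transport.
- A reader might see a contradiction between Section 8 and Section 10. Section 10 says "In all cases where a new medication is commenced we will inform" the treating physician, and the letter to physicians in the same section says "Where there is a need to prescribe medications, we will seek your agreement prior to prescribing". Both speak of starts, but Section 8 item 6 already covers notification and risk discussion for stops. The passages differ in scope and do not conflict. Whether the prior-agreement wording is meant to reach stopped drugs is a question for the investigators.
- A reader might want a count of affected deaths. The documents give neither an expected mortality nor a frequency of stopping drugs, so any count would rest on invented inputs.

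None of this supplies the missing wording. Regular reporting of a death is not the 24-hour full report. The first-month joint review covers events already recorded as adverse or serious adverse events, and only for that month.

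**Conclusion.** The point holds as a gap in scope. Section 8 item 6 makes both starting and stopping drugs part of what the team does and treats both as carrying risk. Section 24 tests a death only against drugs prescribed or recommended, and its trigger names only prescription. A death that the team attributes to its own discontinuation of a drug, or to a non-drug component of the intervention, therefore has no written route to SAE status or to the 24-hour full report.

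The size can be given only in kind: one of the two medication actions in item 6, plus the non-drug components, lies outside the written test. The conclusion rests on a literal reading of Section 24, on Section 10 labelling death as expected, and on the monitoring plan not already covering the gap. If that plan does cover it, the protocol should be brought into line with it. The discontinuation limb is explicit in the text. The non-drug limb is an inference from the review being limited to medications, and it is the weaker of the two.

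**What to change.** In Section 24, *Specific Items That Will Be Monitored for Safety*, change two sentences:

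- Widen the review of each death to *any medication started, changed or stopped by, or on the advice of, the study team, or any other component of the study intervention*.
- Make the trigger match: *a causal relationship between the study team's action and the death*.

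Add that stops and changes will be identified from the intervention team's encounter records in the electronic medical record, with the abstracted medication lists as support. Check the data safety monitoring plan for the same scope and align the two documents. Ask the investigators to state whether the prior-agreement wording in Section 10 is meant to cover stopped drugs. That is a clinical decision and no answer is proposed here.

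The cost is small. Every death is already reviewed and the encounters are already recorded. The added burden is a somewhat wider chart review per death, and possibly a few more deaths reported as SAEs.
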